Sample size and power considerations

The sample size calculation applies jointly to both primary efficacy objectives. A power analysis for comparing two proportions using Pearson’s chi-square test indicated that, with a 1:15 allocation ratio between groups, a total sample size of 992 would provide 92% power to detect a 20 percentage point absolute difference (0.80 vs. 0.60) at a two-sided significance level of 5% ($\alpha = 0.05$). The calculation employed a normal approximation to the binomial distribution under the null hypothesis of no difference in proportions. For practical and operational considerations, the sample size was rounded up to 1000 participants to ensure sufficient power and account for potential deviations.

Framework

Both primary and secondary outcomes are analysed within a superiority framework; surgical interventions are favourable compared to non-surgical interventions.

Statistical interim analysis and stopping guidance

No statistical interim analysis is planned on the primary endpoint.

Timing of final analysis

Data extraction and analysis for the between-group comparison (Surgical vs. Non-Surgical) for the primary endpoint (1 year follow-up) is planned to be performed after making this SAP public available. The main publication of the trial will be prepared when these data have been received and cleaned (anticipated by September 2025).

Timing of outcome assessments

The overview of trial procedures and time-point of each outcome assessment is presented in the **Illustration 2** “Timeline for recruitment and follow-up” and **Box 1** “Outcomes and Covariates – Timepoint of assessment”. The Treatment allocation date (Surgical or Non-surgical) is used to calculate 3 months, 6 months and 1 year follow-up time points.

[figure not shown]

Illustration 2: Timeline for recruitment and follow-up. -t₂: 2-4 days prior to medical examination; -t₁=Day of medical examination; t₀=Allocation; t₁= 3 months; t₂= 6 months; t₃= 1 year.

STATISTICAL PRINCIPLES

Confidence intervals and p-values

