All statistical tests and 95% confidence intervals (95%CIs) will be two-sided and *p-value* < 0.05 will be considered statistically significant for the primary and co-primary endpoint. Groups will be considered comparable if the two-sided 95% confidence interval for the odds ratio comparing Shoulder Surgery with Nonoperative Treatment, for both the primary and co-primary endpoint, lies entirely within the range of 0.80 to 1.25.²⁷ In the secondary outcomes Quick-DASH and VAS, a 95% confidence interval excluding a difference greater than 10 Quick-DASH points or 10 points on VAS between the two groups will be interpreted as indicating absence of a minimal clinically important difference (i.e. possible equivalence).

To address multiplicity, a gatekeeping procedure will be applied to both the primary objectives and the key secondary objectives to determine which will be used in the interpretation of the study results. While all outcomes will be analysed and presented, only those passing the gatekeeping procedure will be considered for inferential conclusions. The gatekeeping procedure follows a hierarchical approach in the prioritised order listed below. Statistical testing will proceed sequentially until an analysis fails to show a statistically significant difference (*p* < 0.05), or until all analyses have been completed.

If a test does not meet the specified statistical significance threshold, no further claims will be made for subsequent outcomes in the hierarchy:

- 1) PASS
- 2) Quick-DASH MIC
- 3) GPE
- 4) Quick-DASH

- 5) Maximum Pain
- 6) Pain in activity
- 7) Pain at rest
- 8) Shoulder related sleep disturbance

Adherence and protocol deviations

Adherence to the surgical intervention is assessed by the percentage of patients being referred to surgery at the initial clinical evaluation, and the actual number of these patients having a record of the surgery was performed in the REDCap database, including date and type of surgery performed: adherence% = (Number of patients with a surgical record in REDCap database/ number of patients referred for surgery at first medical examination) x 100.

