The co-primary endpoint is the proportion of participants achieving a reduction greater than 41%, corresponding to a minimal important change,³⁵ in their Quick-DASH score from baseline to 1 year post allocation (Quick-DASH MIC). This binary endpoint (achieved/not achieved) reflects whether an individual's improvement surpasses the defined clinically important change. A higher proportion of patients reaching this threshold indicates a more favourable treatment effect on physical function and symptoms.

Key Secondary:

The following key secondary outcomes will be analysed to assess the between-group differences in treatment effects over time. Unless otherwise stated, the primary analysis time point for all key secondary outcomes is 1 year after treatment allocation. Additional measurements will be taken at 3 and 6 months for descriptive and exploratory analyses of trajectories over time.

1. Global Perceived Effect (GPE)

Outcome:

Patient-reported global impression of change in "Overall shoulder problems", measured using a 15-point Likert scale ranging from "A great deal worse" (score = 1) to "A great deal better" (score = 15).

Endpoint:

The participants answer on the GPE question “All in all, how do you experience your shoulder problems now compared to before you started your treatment in the study?” will be dichotomised into “Improved” (score > 9) and “Not improved” (score ≤ 9). The key secondary endpoint is the proportion of participants classified as “Improved” at 1 year after treatment allocation. The GPE has been shown to be a valid and reliable outcome measure in shoulder trials and is recommended by OARSI.^{36 37}

2. QuickDASH Score

Outcome:

Self-reported upper extremity disability and symptom severity, measured using the 11-item Quick Disabilities of the Arm, Shoulder and Hand (QuickDASH) questionnaire.³⁴ Each item is rated on a 5-point Likert scale and transformed into a total score ranging from 0 (no disability/symptoms) to 100 (most severe disability/symptoms). The optional work and sports/music modules are excluded from the analysis. The QuickDASH has demonstrated high reliability, validity, and responsiveness in patients with shoulder conditions.^{34 35}

Endpoint:

The key secondary endpoint is the between-group difference in change in total QuickDASH score from allocation to 1 year follow-up. The outcome will also be measured at 3 and 6 months for secondary analyses.

3. Shoulder Pain Intensity variables

Outcome:

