The primary analyses will be based on the Intention to Treat (ITT) population. Categorical endpoints (e.g., the proportion achieving PASS/Quick-DASH MIC after 1 year) will be analysed using logistic regression, with treatment group and stratification factors as covariates, based on the IPW data provided initially. The primary estimand will be the odds ratio (OR) with 95% confidence intervals (CIs) derived from the fully adjusted logistic regression model. The main analysis will use inverse probability weighting, with further adjustment for stratification variables. The OR will represent the treatment effect, with CIs providing the range within which the true treatment effect is expected to lie with 95% certainty. A p-value will be reported to assess the statistical significance of the treatment effect, testing the null hypothesis of no difference between groups. An OR >1 indicates higher odds of achieving the PASS/Quick-DASH MIC outcome with surgical treatment, while an OR <1 indicates lower odds. For secondary objectives, categorical outcomes will be analysed using the same approach as the primary endpoints, while continuous outcomes will be analysed as change from baseline using repeated-measures mixed-effects linear models. Patient identification number will be included as a random effect. Fixed effect factors will include baseline score, treatment group (Shoulder Surgery vs Nonoperative Treatment), time point (baseline, 3, 6, and 12 months), stabilised inverse probability of treatment weighting (sIPTW), and treatment-by-time interactions.

Sensitivity analysis will be performed with the purpose to test the robustness of the primary analyses, based on the per-protocol population, if $>5\%$ of the total number of patients in one treatment group are major protocol violators. The per-protocol analysis set will include: 1) patients who in the surgical group were 'allocated (initial clinical decision at first medical examination) to receive surgery, and have a record of the surgery was performed in the REDCap database, including date and type of surgery performed, 2) patient who in the non-surgical group were allocated (initial clinical decision at first medical examination) to receive non-surgical treatment and a minimum of 1 record, in the REDCap database, of receiving non-surgical intervention after the initial clinical examination as well as no record of surgery performed.

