Morphine or opioids — no. (%)

Other — no. (%)

Diagnostic group

Degenerative — no. (%)

Non-Specific shoulder pain — no. (%)

Non-traumatic instability/luxation — no. (%)

Traumatic injury — no. (%)

Quick-DASH score‡ — 0 to 100

VAS Shoulder pain Maximum§ — 0 to 100

VAS Shoulder pain Activity§ — 0 to 100

VAS Shoulder pain Rest§ — 0 to 100

VAS Shoulder related sleep

Disturbance§ — 0 to 100

* Plus-minus values are mean \pm SD unless otherwise indicated.† The Danish Health Authority guideline recommends alcohol consumption lower than 7 units per week for females and 14 units per week for males to have a low risk of developing diseases.⁴⁸

‡ The short version of the Disability of the Arm, Shoulder and Hand Questionnaire (Quick-DASH) ranges from 0 to 100, with higher scores indicating worse disease status.

§ Visual Analog Scale (VAS) ranges from 0 to 100, with higher scores indicating worse status.

Table 2. Primary and Key Secondary Outcomes at 1 year in the Intention-to-Treat Population.*

VARIABLE	SURGICAL GROUP	NON-SURGICAL GROUP		BETWEEN GROUP	
		OR (95%CI)		Crude	Adj.
PRIMARY OUTCOME					
PASS - no. (%)					
QUICK-DASH MIC - no. (%)					
KEY SECONDARY OUTCOME					
GPE - OVERALL SHOULDER PROBLEMS - no. (%)					

	Mean change from baseline	SE	Mean change from baseline	SE	LSMean difference (95% CI)	
					Adj.	p-value
Quick-DASH - 0 to 100						
VAS SHOULDER PAIN MAXIMUM - 0 to 100						
VAS SHOULDER PAIN ACTIVITY - 0 to 100						
VAS SHOULDER PAIN REST - 0 to 100						
VAS SLEEP DISTURBANCE - 0 to 100						

PASS: Patient Acceptable Symptom State; GPE: Global Perceived Effect; Quick-DASH: Short form of Disability of the Arm, Shoulder and Hand questionnaire; VAS: Visual Analog Scale. * All analyses will be based on the ITT population: For dichotomous outcomes, logistic regression will be applied, with treatment group and stratification factors as covariates, based on the IPW data (missing data at 1 year from allocation will be addressed through non-responder imputation); The primary estimate will be the odds ratio (OR) with 95% confidence intervals (CIs) derived from the logistic regression model. For continuous outcomes, repeated measures linear mixed effects models (with no imputation for missing data) will be applied; Estimates are mean change from baseline and standard deviations with difference between groups reported with 95% confidence intervals.

Figures:

[figure not shown]

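### The change-from-baseline model for the five continuous key secondary outcomes counts baseline as an outcome time point, which dilutes the baseline adjustment and, with a pooled residual variance, narrows the 1-year intervals

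*SAP*

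**What the plan says.** The SAP's Analysis methods section fixes the model in three consecutive sentences.

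- The outcome scale: "continuous outcomes will be analysed as change from baseline using repeated-measures mixed-effects linear models".
- The covariance: "Patient identification number will be included as a random effect".
- The fixed effects: "Fixed effect factors will include baseline score, treatment group (Shoulder Surgery vs Nonoperative Treatment), time point (baseline, 3, 6, and 12 months"), followed by "stabilised inverse probability of treatment weighting (sIPTW), and treatment-by-time interactions".

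The target is a single contrast at 1 year. For Quick-DASH the endpoint definition reads "The key secondary endpoint is the between-group difference in change in total QuickDASH score from allocation to 1 year follow-up"; the pain and sleep scales are defined in the same way. Table 2 reports it as an adjusted "LSMean difference (95% CI") with a p-value. Under Confidence intervals and p-values, these results feed items 4 to 8 of the hierarchy. They also feed a second reading, in which "a 95% confidence interval excluding a difference greater than 10 Quick-DASH points or 10 points on VAS between the two groups" is taken as possible equivalence.

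Analysis methods, Missing data and the Table 2 footnote state no baseline-by-time interaction, time-specific residual variance, unstructured covariance or robust variance.

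**The concern.** Change from baseline exists only after baseline. If baseline is kept as a level of the time factor, every patient in both groups contributes a row with outcome zero, no variance and no relation to the baseline score. Two things follow.

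- **Adjustment.** The model has one baseline-score slope for all rows. A quarter of the rows have a true slope of zero, so the fitted slope is too shallow and part of any baseline difference stays in the treatment effect.
- **Precision.** If one residual variance is pooled over rows, the zero-variance rows lower it, and the 1-year standard error with it.

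Adjustment matters here because allocation follows clinical judgement, so the groups may well differ in severity. Box 1 is said to hold the full propensity covariate list. It shows baseline Quick-DASH and VAS only among the outcome measures, not among the de-confounding covariates. The baseline-score term is therefore the only explicit adjustment for the baseline value of each continuous outcome, and it is the term that the zero rows dilute.

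**Working it through.** **Inputs from the SAP.** Sample size and power considerations states that "a total sample size of 992 would provide 92% power to detect a 20 percentage point absolute difference (0.80 vs. 0.60"), at 1:15 and two-sided 5%. That gives 992/16 = 62 surgical and 930 non-surgical patients.

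**The plan's own figure.** The SAP gives no figure for the continuous model; the power statement supplies only the arm sizes. With h = 1/62 + 1/930 = 0.01720:

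- pooled proportion = (62 × 0.80 + 930 × 0.60)/992 = 0.6125
- SE under the null = √(0.6125 × 0.3875 × h) = 0.0639
- SE under the alternative = √(0.16/62 + 0.24/930) = 0.0533
- power = Φ[(0.20 − 1.96 × 0.0639)/0.0533] = Φ(1.40) = 0.920, which reproduces the stated 92%.

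**Assumptions not in the SAP.** Score SD σ = 20 at every visit; baseline-to-follow-up correlation ρ = 0.3 to 0.5; correlation among follow-ups r = 0.5 to 0.7; complete data; no weighting; one residual variance; model-based SEs; no true effect.

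**Step 1: slope.** At each follow-up, change regresses on baseline with slope ρ − 1; at the baseline row the slope is 0. The fitted slope is the average over four rows, ¾(ρ − 1):

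- ρ = 0.5: −0.375 instead of −0.50
- ρ = 0.3: −0.525 instead of −0.70

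**Step 2: bias.** The unadjusted part of a baseline imbalance d is (1 − ρ)/4 × d, in favour of the group that is worse at baseline:

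- d = 5: 0.125 × 5 = 0.6 points (ρ = 0.5); 0.175 × 5 = 0.9 (ρ = 0.3)
- d = 10: 1.25 points (ρ = 0.5); 1.75 (ρ = 0.3)

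**Step 3: standard error of the 12-month LSMean difference.** For a balanced random-intercept fit with four rows:

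- model variance = h × (V + ¾W), where V is the residual variance of the patient mean after baseline adjustment and W is the pooled within-patient mean square
- true variance = h × [σ²(1 − ρ²) + ((1 − ρ)/4)²σ²]

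With ρ = 0.5 and r = 0.7, each follow-up residual has variance 300 and covariance 180; each change has variance 400 and covariance 280.

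- V = (3 × 300 + 6 × 180)/16 = 123.75
- W = [3 × 400 − (3 × 400 + 6 × 280)/4]/3 = 160
- model SE = √(0.01720 × (123.75 + 120)) = 2.05
- true SE = √(0.01720 × (300 + 6.25)) = 2.30
- ratio 0.89

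In general the variance ratio is (15 + 9ρ)/(17 + 15ρ); r cancels. At ρ = 0.3 it is 17.7/21.5 = 0.823, so the SE ratio is 0.91 (2.31 v 2.54).

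**Step 4: type I error.** This is Φ(−1.96k + b/s) + Φ(−1.96k − b/s), with k the SE ratio, b the bias and s the true SE.

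| Baseline imbalance | ρ = 0.3 | ρ = 0.5 |
|---|---|---|
| 0 points | 7.5% | 8.0% |
| 5 points | 9.3% | 9.2% |
| 10 points | 14.5% | 12.5% |

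**Step 5: simulation check.** With 3,000 simulated trials per scenario, the slopes were those of Step 1. The closed-form fit matched a standard mixed-model routine on a test data set. With no imbalance and ρ from 0.3 to 0.7, the SE ratio was 0.88 to 0.90 and coverage 91.3% to 92.5% (type I error 7.5% to 8.7%). At ρ = 0.5, r = 0.7 and a 10-point imbalance, coverage was 87.1%.

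**Step 6: the same model on 3, 6 and 12 months only.** The slope is recovered in full, the SE ratio is 0.98 to 1.01, coverage is 94.0% to 95.7%, and there is no bias under imbalance. The SE becomes √(0.01720 × 300) = 2.27 at ρ = 0.5 and √(0.01720 × 364) = 2.50 at ρ = 0.3. Intervals widen by 2.27/2.05 = 1.11 and 2.50/2.31 = 1.08.

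**The case against.** Several points on the other side are sound.

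- **The figures are not for the planned analysis.** The SAP uses stabilised inverse probability weights, and the illustration is unweighted. SD, correlations and imbalance are assumed, and a 10-point imbalance is half the assumed SD. The figures show direction and rough size only.
- **Narrow intervals are conditional.** The SAP names a patient random effect but no residual structure or variance estimator. A sandwich variance would largely repair the interval, though not the diluted slope. If the treatment-by-time coefficient against baseline were reported instead, the narrowing could almost vanish (SE ratio 0.99 when all correlations are 0.5). Baseline score then drops out altogether, however, with a bias of about 2.5 or 5 points for a 5- or 10-point imbalance at ρ = 0.5. Table 2 points to the LSMean difference.
- **Residual plots are planned.** They might expose a zero-variance row, but no corrective action is stated.
- **The reach is limited.** Items 4 to 8 support a superiority claim only if PASS, Quick-DASH MIC and GPE are all significant first. At ρ = 0.5 the interval half-width moves by 1.96 × (2.30 − 2.05) = 0.5 points, and the bias is 0.6 to 1.25 points, against a 10-point margin. The 10-point reading would rarely change.
- **The factor of three quarters assumes complete data.** The SAP expects some missing follow-up.

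One defence fails. If the raw score was meant as the outcome, the outcome at the baseline row would equal the baseline-score covariate, so the specification would still contradict itself.

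**Conclusion.** The specification is wrong as written and should be fixed. It combines two incompatible models: change with baseline as covariate, and a response series that includes baseline. The dilution of the baseline slope follows from the text, and its factor of three quarters from complete data. The too-narrow interval follows if the residual variance is pooled and the SEs are model-based.

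Under the assumptions listed, the SE is about 8-12% too small. Type I error is about 8-9% with no baseline imbalance, 9-10% with 5 points (bias about 0.6-0.9) and 12-15% with 10 points (bias about 1.2-1.8), against a nominal 5%.

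A reader might infer that the trial's main results are compromised, or that the intervals are too narrow whatever the software settings. The document supports neither. PASS, Quick-DASH MIC and GPE are analysed by logistic regression and are untouched, and the variance estimator is left open. Nor do the figures forecast this trial's error rate, since the baseline imbalance left after weighting is unknown.

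**What to change.** In the SAP's Analysis methods section, list the time factor as 3, 6 and 12 months. Keep change from baseline as the outcome and baseline score as covariate. A baseline-by-time term is optional. The 1-year time point for the key secondary outcomes is already stated and needs no new text.

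Do not switch to raw scores at all four times with the baseline covariate dropped and no constraint on the baseline means. In these non-randomised groups, the 12-month contrast then becomes a plain difference in change scores. Its bias is (1 − ρ) × d, four times that of the faulty model: 2.5 and 5 points, against 0.6 and 1.25, for imbalances of 5 and 10 points at ρ = 0.5.

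The cost is one line of wording and no new data. Intervals become about 10% wider, which is their correct width. The change should be made before the data are analysed, so that the model is not chosen after the results are seen.

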To analyse observational data for causal treatment effects, the most important methodological challenge is to control bias due to lack of randomisation. With the rising challenge of analysing more complex observational data, the propensity score has been the foundation for many of these approaches. Bias control methods based on propensity scores have become widely accepted. To define the propensity score, we introduce the following notation: let $X = (X_1, \dots, X_n)$ represent n confounders that are measured prior to intervention initiation (referred as “baseline confounders” below), then $X_i = (X_{1i}, \dots, X_{ni})$ is a vector of the value of the n confounders for the i^{th} subject. Let T represent the available interventions, with $T = 1$ indicating the subject is in the group initially allocated to surgery and $T = 0$ meaning the subject in the control group (ie, referral to non-surgical intervention). For the i^{th} subject, the propensity score is the conditional probability of being in the treated group given their measured baseline confounders,

$$\text{Prob } (X_i) = (T_i = 1 \mid X_i)$$

Intuitively, the propensity score provides a way to simulate randomisation when actual randomisation is not feasible. By conditioning on the propensity score, we aim to ensure that each subject has an equal chance of receiving treatment, thereby balancing the distributions of measured baseline confounders between treatment and control groups. The stabilized inverse probability treatment weighting (sIPTW) approach will be used as the analysis. A multivariable binomial logistic regression model will be utilised to generate the propensity scores.

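### The mixed model for the five continuous key secondary endpoints takes the stabilised weight as a fixed effect, which leaves the confounding in place, and it keeps baseline as a time level of a change score

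*SAP*

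**What the plan says.** Under Analysis methods, the SAP defines the propensity score and then states: "The stabilized inverse probability treatment weighting (sIPTW) approach will be used as the analysis". Binary endpoints follow this. The Table 2 footnote says that "logistic regression will be applied, with treatment group and stratification factors as covariates, based on the IPW data".

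For the continuous key secondary endpoints, the same section says that "continuous outcomes will be analysed as change from baseline using repeated-measures mixed-effects linear models", with patient as a random effect. The fixed effects are baseline score, treatment group, and then "time point (baseline, 3, 6, and 12 months), stabilised inverse probability of treatment weighting (sIPTW), and treatment-by-time interactions". The diagnostic strata are not in this list.

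The Table 2 footnote describes this model without any weighting: "For continuous outcomes, repeated measures linear mixed effects models (with no imputation for missing data) will be applied". Table 2 reports the result as an adjusted least-squares mean difference. Under Confidence intervals and p-values, "a 95% confidence interval excluding a difference greater than 10 Quick-DASH points or 10 points on VAS between the two groups" is to be read as absence of a minimal clinically important difference. These five endpoints are items 4 to 8 of the testing hierarchy.

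**The concern.** There are two faults in one sentence of the plan.

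1. **Role of sIPTW.** A term in a fixed-effect list is a regressor. An inverse probability weight removes confounding by re-weighting patients, not by being regressed on. If it does nothing as a regressor, baseline score is the only adjustment left, and the Box 1 covariates (imaging, examination findings, treatment preference, expectation and the rest) play no effective part.
2. **Baseline as a time level.** Change from baseline is 0 at baseline for every patient. Those rows carry no information on treatment, but they enter the variance estimate and the common baseline-score slope.

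Five of the eight hierarchy items would then be labelled adjusted and read against a 10-point margin with at most baseline score adjusted for. No other planned analysis would show the problem: the per-protocol sensitivity analysis changes only the population, and no additional analyses are planned.

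**Working it through.** **Inputs from the SAP.** Total 992 at 1:15 (Sample size and power considerations), so 992/16 = 62 surgical and 930 non-surgical. The plan's own power figure reproduces. The pooled proportion is (62×0.80 + 930×0.60)/992 = 0.6125. The null SE is sqrt(0.6125×0.3875×(1/62+1/930)) = 0.0639 and the alternative SE is sqrt(0.16/62+0.24/930) = 0.0533. Power is Φ((0.20 − 1.96×0.0639)/0.0533) = 92%. That figure is not at issue; only the group sizes are used below.

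**Inputs assumed (the SAP gives none).** True effect 0; 1 in 16 treated; one confounder worth 8 points per SD; propensity c-statistic 0.64 to 0.75; correlation of confounder with baseline score 0.3 to 0.9; SD of change 20.

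**Step 1: algebra.** Let e(X) be the true propensity score, p the treated share and B the baseline score, with B part of X. The stabilised weight is w = p/e(X) in the treated and (1−p)/(1−e(X)) in the untreated.
- E[w | T=1] = ∫ (p/e)·(e·f(x)/p) dx = 1, and likewise E[w | T=0] = 1. Hence Cov(w,T) = p·1 − 1·p = 0.
- By the same step E[wB] = E[B]. Hence Cov(w,B) = 0.

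So w is uncorrelated with treatment after regression on B, and adding it as a linear covariate cannot move the treatment coefficient. This does not depend on how strong the confounding is.

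**Step 2: size under the assumptions.** 400,000 patients per scenario, visits at 3, 6 and 12 months, between- and within-patient variances 240 and 160, baseline score in the model. Bias in the 12-month treatment effect, in points:

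| c-statistic | corr. 0.3 | corr. 0.6 | corr. 0.9 |
|---|---|---|---|
| 0.64 | 3.51 | 2.46 | 0.82 |
| 0.71 | 5.79 | 3.98 | 1.15 |
| 0.75 | 6.98 | 4.68 | 1.45 |

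- sIPTW added as a covariate: the same to two decimals in all nine cells.
- sIPTW as a patient-level weight: −0.22 to 0.24.
- Weights that scale only the residual variance of the mixed model: 0.68 to 5.56, so most of the bias stays.

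**Step 3: trial size, estimated score.** With N = 1000, 1:15, 1 to 30 confounders and 5 points per SD, the covariate form made the bias slightly larger, by 1.6% to 2.4% (3.30 to 3.35; 4.11 to 4.20). Weighting removed about 86% to 99%. In a large-sample check with a misspecified propensity model and a true effect of −6, the covariate form moved the estimate from −3.27 to −3.32 and from −2.64 to −2.67; weighting gave −5.94 and −5.32.

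**Step 4: baseline rows and the SE.** With variance 400 at three visits and 0 at baseline, the pooled variance is (3×400 + 0)/4 = 300.
- Least-squares mean contrast: sqrt(300×(1/62+1/930)) = 2.27, against sqrt(400×(1/62+1/930)) = 2.62. The shortfall is 1 − sqrt(3/4) = 13.4% at any within-patient correlation, and the size of a nominal 5% test is about 9%. Mixed models fitted at N = 992 and correlation 0.6 gave mean SEs of 2.26 and 2.62.
- Treatment-by-time contrast (12 months against baseline): with correlation r between follow-up visits, only 3 of the 6 visit pairs have covariance 400r, so the between-patient component is 200r and the residual is s² = 300 − 200r. The SE is sqrt(2s²(1/62+1/930)): 2.87 at r = 0.3 (s² = 240), 2.62 at r = 0.5, 2.19 at r = 0.8 (s² = 140). Test size runs from 3.2% to 10.1%, so the error can go either way.

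**Step 5: baseline rows and the adjustment.** The common baseline-score slope averages three follow-up slopes and a zero, so it falls to 3/4; the simulation gave 0.750 in all nine scenarios. In the treatment-by-time contrast, baseline score cancels altogether. In one scenario the crude difference was 4.77 and the estimate without baseline rows 5.61. With baseline rows, the least-squares mean contrast was 4.77 + 0.75×(5.61 − 4.77) = 5.40 and the treatment-by-time contrast 4.77, equal to the crude difference.

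**The case against.** The best defence is that this is loose drafting. The SAP declares weighting as the analysis before it separates endpoint types, and the listed term names a procedure rather than a variable. A further sentence in Analysis methods says the main analysis uses inverse probability weighting with adjustment for the stratification variables. A weighted model may well have been meant. But that sentence stands among the odds-ratio text, and the Table 2 footnote ties the weighted data to dichotomous outcomes only. Nothing corrects the fixed-effect list, and a programmer who follows it gets the wrong model. Saying only that the model is weighted would not settle the matter either, as the residual-variance result in Step 2 shows.

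Two technical caveats stand. First, weights average 1 per arm only in large samples with a correct score. At N = 992 with about 63 treated, the mean weight in the treated was 1.01, 1.08 and 1.36 with 30, 60 and 75 covariates. The covariate form still left the bias (3.77 became 3.88 with 60; 4.23 became 4.33 with 75). Second, proper weighting costs precision. In a single-visit check at that size, the SD of the estimate rose from about 2.6 to 4.1, 5.2 and 6.6, and with 75 covariates the root mean squared error (about 6.6) exceeded that of the unweighted estimate (about 5.0). That is a reason to keep the propensity model small, not to regress on the weight.

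The stakes are also limited. The primary and co-primary endpoints and GPE do not use this model, and each of items 4 to 8 carries a claim only if every earlier item has passed.

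**Conclusion.** The concern holds and should be fixed. Read as written, sIPTW in the fixed-effect list contradicts the SAP's declared method and removes essentially none of the confounding that baseline score leaves. The near-zero removal rests on algebra for a correct score, and estimated or misspecified scores shifted the remaining bias by about 2% or less. The bias in points (0.82 to 6.98) rests wholly on the assumed confounder strengths and is an illustration, not an estimate for this trial.

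The baseline rows are a separate error in the same sentence. The 13.4% shortfall in the least-squares mean SE assumes complete data, equal variances across follow-up visits, a random intercept and model-based SEs. It is the relevant figure if Table 2's least-squares mean difference is the reported contrast.

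**What to change.** In Analysis methods:
- Delete sIPTW from the fixed effects. State that the repeated-measures model is fitted with sIPTW as a patient-level weight, for example by weighted pseudo-likelihood or weighted GEE and not by weights that scale only the residual variance. Specify robust or bootstrap variance. If GEE is chosen, say how the missing-at-random assumption in the Missing data section is kept.
- Use 3, 6 and 12 months as the time levels, with baseline score and diagnostic group as covariates, and name the 12-month treatment contrast as the estimate.

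In the Table 2 footnote, state the weighting for continuous outcomes as well.

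The cost is SAP wording and a few lines of code, with no new data. Expect wider confidence intervals than an unweighted model would give.
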